

Study Part	Cohorts	Dose Regimen	

Phase I	Dose Escalation	INXN-2001: [REDACTED] INXN-1001: 5, 20, 100, 160 mg	

Group 1	INXN-2001: [REDACTED] INXN-1001: 160 mg daily for 7 consecutive days; 21-day cycle	

Phase II	Group 2	INXN-2001: [REDACTED] INXN-1001: 160 mg every other day for 14 days; 28-day cycle	

		Study Part	Cohorts	Dose Regimen	Phase I	Dose Escalation	INXN-2001: [REDACTED] INXN-1001: 5, 20, 100, 160 mg	Group 1	INXN-2001: [REDACTED] INXN-1001: 160 mg daily for 7 consecutive days; 21-day cycle	Phase II	Group 2	INXN-2001: [REDACTED] INXN-1001: 160 mg every other day for 14 days; 28-day cycle
Study Part	Cohorts	Dose Regimen										
Phase I	Dose Escalation	INXN-2001: [REDACTED] INXN-1001: 5, 20, 100, 160 mg										
	Group 1	INXN-2001: [REDACTED] INXN-1001: 160 mg daily for 7 consecutive days; 21-day cycle										
Phase II	Group 2	INXN-2001: [REDACTED] INXN-1001: 160 mg every other day for 14 days; 28-day cycle										
In Phase I, four sequential dose escalation cohorts of INXN-1001 in combination with a fixed dose of INXN-2001 are planned (Table 1). Subject enrollment and dose escalation will proceed according to a standard 3+3 design. In each cycle, the subjects will be treated with one intratumoral injection of INXN-2001 in combination with 7 oral doses of INXN-1001. No intrasubject dose escalation will be allowed.	
[Please refer to Appendix 5 for additional study design details for the Phase I and Phase II, Group 1 portions of this study.]
											
	
In Phase II, approximately 15 additional subjects will be enrolled at a single dose level at or below the MTD. Phase II of the study will include two groups of subjects. Subjects enrolled in the Phase II portion of the study under Amendment 6 or prior will be enrolled into Group 1; subjects enrolled under Amendment 7 or later will be enrolled into Group 2.
											

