5.5 RATIONALE FOR STUDY DESIGN AND DOSE SELECTION

The objectives of this Phase I/II clinical trial are to assess the safety, objective response rate, and immunological and biological effects of intratumoral injections of INXN-2001 in combination with escalating dose levels of oral INXN-1001. The dose escalation portion of the study (Phase I) uses a standard 3+3 design commonly used in Phase I studies of investigational anticancer therapies. To provide an opportunity to monitor the safety of the combination therapy, there will be at least 7 days between the initiation of treatment for the sentinel (first) subject and additional subjects in all cohorts during the dose escalation stage of the study. Phase II will be enrolled (approximately 15 subjects) at or below the MTD and using two groups. One group will receive an INXN-1001 daily for 7 days dosing regimen, and the other group will receive an every other day dosing regimen for 14 days to compare tolerability of INXN-1001 at the 160-mg dose.

Phase I: In each of six 21-day cycles, the subjects will receive one intratumoral injection of INXN-2001 in combination with 7 oral daily doses of INXN-1001.

Phase II, Group 1: In each of six 21-day cycles, the subjects will receive one intratumoral injection of INXN-2001 in combination with 7 oral daily doses of INXN-1001.

Phase II, Group 2: In each of six 28-day cycles, the subjects will receive one intratumoral injection of INXN-2001 in combination with 7 oral doses of INXN-1001 administered every other day for 14 days.

The INXN-1001 dose levels to be studied (5 to 160 mg/day) are within the range of doses administered in previous human clinical trials [REDACTED] and are expected to provide plasma levels that are biologically effective for [REDACTED] activation. Although good safety and tolerability is expected based on previous clinical experience, rigorous safety monitoring during the course of this study will be performed by the Safety Review Committee (SRC).

In all treatment cycles throughout the study, the INXN-2001 dose will be fixed [REDACTED] dose. This dose was selected based on: (i) preclinical studies that indicated that this would be within an effective range, and (ii) previous clinical trials of administered adenoviral vectors [REDACTED]

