6.2.4 Definition and Management of Dose-Limiting Toxicity (DLT)

Dose-limiting toxicity (DLT) is defined as:

- Any injection site reaction that includes ulceration, necrosis, severe tissue damage or where operative intervention is required.
- Any local or systemic injection reaction that has life-threatening consequences, requires urgent intervention or results in death.

- Any study drug-related \geq Grade 3 adverse event, except nausea and/or vomiting in subjects who did not receive optimal treatment with anti-emetics.

Phase I and Phase II, Group 1: If DLTs have been observed in >1 of the 3-6 subjects in a cohort during the first treatment cycle, the MTD will have been exceeded and further use of that dose will be discontinued in all subjects, and the next lower dose cohort will be assessed as to whether it meets the definition of the MTD.

Phase II, Group 2: If an adverse event that meets the Phase I DLT definition is observed in >1 of the 3-6 subjects in Group 2 during the first treatment cycle, the SRC will convene to discuss reduction in dose and/or change to posology and the cohort will be expanded by 3 subjects. The recommended Phase II dose will be the dosage and posology where ≤ 1 of 3 to 6 subjects experiences an adverse event as described in the definition of DLT.

The Medical Monitor should be immediately notified of any potential DLT. Subjects will be withdrawn from study treatment if they experience an injection site reaction that meets DLT criteria or other Grade 3 toxicity related to study drug that, upon review of the SRC, is deemed to be a DLT. If, however, the subject has experienced a substantial benefit from treatment and the SRC recommends continuation on the study, re-exposure to the experimental treatment may proceed at a lower dose of INXN-1001 on a case by case basis. Any subject who experiences a Grade 4 toxicity related to study treatment will be withdrawn from study.

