10.3 STATISTICAL METHODS

Categorical data will be summarized using counts and percentages based on non-missing values. For continuous variables, the mean, median, standard deviation, minimum and maximum values will be presented.

Data will be summarized by dose cohort based on the actual dose of INXN-1001 received on Day 1, Cycle 1. For Phase II, data will be summarized based on group and dose regimen.

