10.3.2 Safety Analyses

The Safety Population will be used for the analyses of safety data based on the dose of INXN-1001 received.

Safety evaluations will be based on the incidence, intensity, and type of AEs and SAEs. Clinically significant changes in the subjects' physical examinations, vital signs, and ECG evaluations, and clinical manifestations relevant to abnormal laboratory values will be captured as AEs. Safety will also be assessed based on medical history and prior/concomitant medications.

AEs will be coded using the Medical Dictionary for Regulatory Activities (MedDRA[®]) for the purpose of summarization. All AEs occurring during the study will be included in by-subject data listings. Treatment-emergent events will be tabulated. 'Treatment-emergent' is defined as any AE that occurs during or after administration of the first dose of study drug through the Post-Treatment Safety Assessment visit (28 days after the last INXN-1001 dose); any event after the first dose of study drug that is considered study drug-related regardless of the start date of the event; or any event that is present at baseline that worsens in intensity or is subsequently considered to be drug related by the investigator. Deaths, SAEs, and AEs resulting in study discontinuation will be listed.

Safety variables will be tabulated and presented by dose cohort. Exposure to study drug and reasons for discontinuation of study treatment will be tabulated.

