Section 8.2.7 Severity Grading and Management of Injection Site Reactions	
Added text:
 
Table 3. Injection Site Reaction Severity Grading and Management
 

CTCA E Grade	Symptoms	Course of Action	

1	Tenderness with or without associated	No intervention required.	

	CTCA E Grade	Symptoms	Course of Action	1	Tenderness with or without associated	No intervention required.	Update language for clarification
CTCA E Grade	Symptoms	Course of Action						
1	Tenderness with or without associated	No intervention required.						

Section in Amended Protocol	Revised or Deleted Text/Section			Rationale for Change
		symptoms (eg, warmth, erythema, itching)		
	2	Pain; lipodystrophy; edema; phlebitis	Proceed with further dosing cycles.	
	3	Ulceration or necrosis; severe tissue damage; operative intervention indicated	Discontinue further study treatment and notify Medical Monitor. Report and manage as DLT: see Section 6.2.4 . If toxicity meets seriousness criteria, immediately report as per SAE reporting procedures; see Section 9.4.	
	4	Life-threatening consequences; urgent intervention indicated	Permanently discontinue study treatment and notify Medical Monitor. Report and manage as DLT: see Section 6.2.4 . Defaults to “serious”. Immediately report as per SAE reporting procedures; see Section 9.4.	
	5	Death	Immediately notify Medical Monitor and report as per SAE reporting procedures; see Section 9.4 . Discontinue further subject enrollment as per study stopping rules; see Section 6.2.7 .	
Section 8.2.8 Prophylactic Hydration , Antipyretic and/or Analgesic Administration	The use of antipyretics and/or analgesics and aggressive hydration is allowed anytime during study treatment, as indicated, including prophylactic administration. Since fever and flu like symptoms are commonly experienced following adenoviral vector administration it is strongly recommended that subjects be treated with prophylactic oral hydration, antipyretic and/or analgesic medications prior to study drug administration.			Add prophylactic hydration along with prophylactic antipyretics and/or analgesics

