10.5 Prior and Concomitant Medication

Medications will be classified according to whether they were being taken pre-study (prior) and/or during the study (concomitant). Prior medications are any that were being taken prior to the first dose of study medication (medication stop date prior to the first dose of study medication). Concomitant medications are any that were being taken on or after the first dose of study medication. If the start and stop dates of the medications do not clearly define the period(s) during which a medication was taken, it will be assumed to be a concomitant medication.

Prior and concomitant medications recorded during the study will be coded using World Health Organization (WHO)-Drug dictionary Q3 2009. Details of prior and concomitant medication will be listed separately.

Prior and concomitant medications will be summarized by preferred term and Anatomical Therapeutic Chemical (ATC) level 2 term.

Tables will be presented by phase only.

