Details of injection reactions including injection site reaction, start/stop date/time, outcome, severity, relation to study drug, treatment required details, injection lesion, whether or not a DLT and seriousness will be listed.

Summaries of injection reactions will be tabulated by type, type by severity and type by relationship to study drug and will be presented by phase only. Relationship to study drug refers to either drug.

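### SAP 12.2 and 10.5 pool injection reactions and concomitant medication by phase, against the protocol's rule of dose cohort and Phase II regimen, and SAP 14.0 does not declare the change

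*SAP*

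**What the plan says.** **Presentation in the SAP.** SAP 12.2 states that the injection-reaction summaries "will be tabulated by type, type by severity and type by relationship to study drug and will be presented by phase only". These are Tables 14.3.2.10 to 14.3.2.12. SAP 10.5 ends with "Tables will be presented by phase only", which covers the concomitant medication table, 14.1.8. The SAP's own default, in section 9.0, is phase and dose cohort, with Phase II by group, Group 2 further by dose cohort, and an overall column per phase. That default applies unless otherwise stated.

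**The protocol's rule.** Protocol 10.3.2: "Safety variables will be tabulated and presented by dose cohort". Protocol 10.3: "For Phase II, data will be summarized based on group and dose regimen". Protocol 10.3.2 also names concomitant medication among the data used to assess safety. Protocol 10.4 requires departures from the protocol's analyses to be indicated in the SAP.

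**Why regimen matters.** Protocol 5.5 says that the two Phase II groups exist "to compare tolerability of INXN-1001 at the 160-mg dose", and informing the choice of dose and regimen is a secondary objective. The first DLT criterion in protocol 6.2.4 is "Any injection site reaction that includes ulceration, necrosis, severe tissue damage or where operative intervention is required".

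**How groups are formed.** There is no randomization (protocol 10.1.1). Group follows the amendment in force: the synopsis says that "subjects enrolled under Amendment 7 or later will be enrolled into Group 2". The summary of changes for Amendment 7 gives as its reason for revising section 8.2.8: "Add prophylactic hydration along with prophylactic antipyretics and/or analgesics". It also records revised antipyretic doses in Appendix 3.

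**The concern.** The injection reaction is the local toxicity most specific to this product, and it can be dose-limiting. The tables that break it down by severity and relationship merge daily with every-other-day dosing, and 160 mg with 120 and 80 mg, so they cannot serve the comparison that protocol 5.5 describes. Nor does the fixed vector dose make pooling harmless: protocol 5.2.2 says that hIL-12 output is modulated by ligand dose and frequency.

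The comparison is also weak by design, because the groups were enrolled one after the other and supportive care was revised in the amendment that opened Group 2. Table 14.1.8 is where recorded antipyretic and analgesic use would be compared between groups, and it merges them too. A reader of the report would see neither the injection-reaction profile by regimen nor this background in tabular form, and the SAP does not say that the layout departs from the protocol.

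**Working it through.** **1. Denominators.** Cohort counts come from SAP 1.0.
- Phase I: 5 mg (3) + 20 mg (3) + 100 mg (3) + 160 mg daily (4) = 13.
- Phase II: 160 mg daily (4) + 160 mg every other day (4) + 120 mg every other day (3) + 80 mg every other day (2) = 13.

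Both agree with SAP 6.1. There is no power calculation to reproduce: protocol 10.1 states that none was done, and SAP 9.0 rules out inferential statistics.

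**2. What each column pools.** Phase II combines 4 daily with 4 + 3 + 2 = 9 every-other-day patients. Phase I spans 160/5 = 32-fold in dose. The 4 + 4 = 8 patients on 160 mg daily are split across the two columns and stand alone in neither.

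**3. What a pooled count leaves open.** Suppose, purely as an illustration, that 4 of 13 Phase II patients have a given reaction. Let a, b, c, d be the counts in the four cohorts, with a ≤ 4, b ≤ 4, c ≤ 3, d ≤ 2 and a + b + c + d = 4.
- Non-negative solutions without the limits on c and d: C(7,3) = 35. Remove 1 with c = 4 and 4 with d ≥ 3, leaving 30 possible splits.
- Daily minus every-other-day rate: lowest 0/4 − 4/9 = −44 points, highest 4/4 − 0/9 = +100 points.
- At 160 mg alone, the 4 could all be daily (4/4 against 0/4) or all every other day (0/4 against 4/4), so the difference runs from +100 to −100 points.
- For 6 of 13, daily minus every-other-day runs from 0/4 − 6/9 = −67 to 4/4 − 2/9 = +78 points.

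Only 0/13 and 13/13 determine the split.

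**4. What splitting gives.** The 160 mg contrast in Phase II becomes visible as 4 against 4, but it stays imprecise.
- Exact 95% upper limit for 0/4: 1 − 0.025^(1/4) = 60.2%. By symmetry, 4/4 has a lower limit of 39.8%.
- Two-sided Fisher, used only as a yardstick: 4/4 against 0/4 gives 2/C(8,4) = 2/70 = 0.029; 3/4 against 0/4 gives 2 × 4/56 = 0.14.

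**5. Is the departure declared?** SAP 14.0 covers objective response rate, duration of response, tumor burden and immunologic correlations. It does not mention injection reactions or concomitant medication.

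**The case against.** The strongest reply is that the information is available elsewhere, and much of this stands.

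- **Other tables.** Protocol 8.2.7 treats reactions at the INXN-2001 site within 24 hours and attributed to it as adverse events, and protocol 9.3 puts all adverse events on the AE page. They should therefore enter the system organ class and preferred term tables, whose percentages are per dose group, and any that are dose-limiting should enter the DLT row of the overall summary, which is per dose cohort within phase and group (SAP 12.2). Listing 16.2.7.8 shows each reaction, and listings are sorted by group and cohort. A reader might infer that a regimen difference would surface only as a pooled fraction of 13; the documents do not support that. What remains is that type by severity and type by relationship are tabulated only in the phase-level tables.
- **Regimen choice.** A reader might infer that selection rests on these tables. It does not: protocol 6.2.4 and 6.2.5 use DLT counts, and SAP 4.4 attributes the reductions to 120 and 80 mg to DLTs.
- **Prophylaxis.** A reader might take the Amendment 7 change as the main explanation for any difference. The amendment summaries show antipyretic prophylaxis strongly recommended from Amendment 2, adequate hydration required from Amendment 5, and oral-hydration instruction strengthened in Amendment 6. Amendment 7 extended and revised these, so the confounding is partial.
- **Limits of Table 14.1.8.** It reports preferred term and ATC level 2. It cannot show dose or whether use was prophylactic, and protocol 8.3 does not mention oral fluids among the data collected.
- **SAP convention.** Section 9.0 allows exceptions, and phase-level tables are also used for medical and oncology history. That settles consistency within the SAP, but the protocol's rule has no such exception and protocol 10.4 asks for departures to be indicated.

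**Conclusion.** The point holds as an undeclared departure in presentation. Three injection-reaction tables and the concomitant medication table are laid out by phase, where the protocol requires dose cohort and, in Phase II, group and regimen. The consequence is that injection-reaction type by severity and by relationship cannot be read by regimen from any planned table: 4 daily patients are merged with 9 every-other-day patients at three doses. No data are lost, and the general adverse-event, Grade 3 or greater, serious-event and DLT summaries keep the dose split.

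This rests on two assumptions. The first is that injection reactions are recorded as adverse events and so reach the general tables; the protocol implies this, but the SAP does not say it. The second is that the tables count patients; SAP 12.2 does not state the unit for these summaries.

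The change is worth making because it restores the protocol's rule at little cost. It will not make the daily against every-other-day comparison precise or unconfounded: it remains 4 against 4 at 160 mg in Phase II, enrolled under successive amendments.

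**What to change.** 1. **SAP 12.2.** For Tables 14.3.2.10 to 14.3.2.12, replace the phase-level presentation with the section 9.0 default of phase, group (Phase II) and INXN-1001 dose cohort. The overall column per phase keeps the current totals.
2. **SAP 10.5.** Do the same for Table 14.1.8, so that recorded antipyretic and analgesic use can be seen by group. Note that it will not show dose, prophylactic intent or oral fluids.
3. **SAP 14.0.** If any of these tables is kept by phase, list it there as a departure from protocol 10.3 and 10.3.2, with the reason.
4. **SAP and study report.** Describe the daily against every-other-day comparison as descriptive, non-concurrent because group was set by amendment, and partly confounded with the prophylaxis revisions in Amendment 7. The amendment each patient was recruited under is already listed (SAP 10.1).

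**Cost.** Changed wording in two SAP sections, extra columns in four tables and a short caveat, with no new data. The tables become wider and cells fall to 2 to 4 patients, which the dose-cohort adverse-event tables already accept.

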12.3 Laboratory Evaluations

Laboratory data for blood chemistry, hematology, and urinalysis will be collected throughout the study.

The following laboratory tests are to be performed as indicated by the schedule of assessments:

| Blood Chemistry | Hematology | Urinalysis |
|----------------------------|--------------------------------|--------------------|
| Albumin | Basophils | Appearance |
| Alanine aminotransferase | | pH |
| Alkaline phosphate | Eosinophils | Specific gravity |
| Aspartate aminotransferase | Platelets | Glucose |
| Bicarbonate | Red blood cell (RBC) | Protein/Albumin |
| Total bilirubin | Hepatitis C Virus | RBC Hgb |
| Blood urea nitrogen | Hemoglobin (Hgb) | Ketones |
| Calcium | Hematocrit | Bilirubin |
| Chloride | International Normalized Ratio | Nitrates |
| Creatinine | Mean corpuscular volume | Leukocyte esterase |
| Gamma glutamyl transferase | Mean corpuscular hemoglobin | |
| Glucose | Neutrophils | |
| Lactic dehydrogenase | Partial thromboplastin time | |
| Potassium | Reticulocytes | |
| Phosphorus | White blood cell | |
| Sodium | | |
| Total protein | | |

Shift tables will be constructed for the clinical chemistry and hematology data showing the shift from the baseline value to the worst (minimum or maximum value) post baseline.

The absolute value and the change from baseline will be tabulated for each scheduled time-point during the study for all continuous urinalysis parameters. Baseline is defined as the Screening value.

Details of clinical chemistry and hematology data will be listed including converted values and showing reference ranges and flagging of abnormal findings and their clinical significance. Out of reference range values will be flagged as high (H) or low (L) in the listing. Laboratory reference ranges will be presented by site.

Pregnancy test details at Screening (serum) and Day 1 of each cycle (urine) will be listed.

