5.4.3 Safety of Intratumoral injection of IL-12 genes

In comparison with administration of recombinant IL-12 protein, injection of plasmids or adenovirus containing hIL-12 genes to cancer patients has proven to limit or abrogate the toxic effects of hIL-12, thus providing an effective way to provide this potent immunomodulatory cytokine. This has been observed in Phase I and II clinical trials where IL-12 is delivered locally, IL-12 levels have been measured systemically in patient serum, and in the majority of these studies, increases in IL-12 serum levels post baseline have not been observed.³¹⁻³³ Numerous studies have shown gene delivery of IL-12 to be well tolerated. In a Phase I dose escalation trial using electroporation to administer plasmid DNA encoding hIL-12 into metastatic melanoma, minimal systemic toxicity and no IL-12-related adverse events were observed in subjects treated at several dose levels.³⁴ Similarly, intratumoral injection of a plasmid DNA encoding human IL-12 (2 to 20 mg of total DNA) in subjects with melanoma was also well tolerated.³⁵ Limited elevations in serum cytokines were observed after treatment. Intra-peritoneal injection of hIL-12 plasmid DNA formulated in polyethyleneglycol-polyethyleneimine-cholesterol (PPC) given to women with chemotherapy-resistant recurrent ovarian cancer also was found to be generally safe and well tolerated. Low-grade fever and abdominal pain were the most common side effects.³⁶ Plasmid DNA was not detected in the patients' serum samples and treatment-related increases in IFN- γ levels were observed only in pleural fluid but not in serum. Similar findings have been obtained with intratumoral injection of adenoviral vectors encoding hIL-12 at doses ranging from 2.5×10^{10} to 3×10^{12} viral particles, to subjects with advanced pancreatic, colorectal, or primary liver malignancies.³¹ Treatment was well tolerated and dose-limiting toxicity was not reached. AEs were transient, with fever, malaise, sweating, and lymphopenia being the most common AEs observed. No cumulative toxicity was observed. All AEs were deemed to be related to injection of the virus and not to transgene expression.

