7.1 INCLUSION CRITERIA

To be enrolled in the trial, each subject must satisfy all of the following inclusion criteria:

1. Males or females of all races \geq 18 years of age, who have provided written informed consent prior to completing any study specific procedure.
2. Unresectable Stage III or Stage IV melanoma arising from any site other than ocular melanoma.
3. A minimum of 2 accessible lesions (shortest diameter \geq 1 cm) or palpable tumor-involved lymph nodes (shortest diameter \geq 1.5 cm).

4. ECOG performance status of 0 or 1 ([Appendix 1](#)).
5. Adequate bone marrow, liver, and renal function, as assessed by the following laboratory requirements:
 - a. Hemoglobin \geq 9 g/L
 - b. Lymphocytes $> 700/\text{mm}^3$
 - c. Neutrophils $\geq 1,500/\text{mm}^3$
 - d. Platelets $\geq 100,000/\text{mm}^3$
 - e. Serum creatinine $\leq 1.5 \times \text{ULN}$
 - f. AST and ALT $\leq 2.5 \times \text{ULN}$. For subjects with documented liver metastases, ALT and AST $\leq 5 \times \text{ULN}$
 - g. Total bilirubin $< 1.5 \times \text{ULN}$
 - h. International Normalized Ratio (INR) and activated partial thromboplastin time [PTT] $< 1.5 \times \text{ULN}$, if not therapeutically anticoagulated. Subjects who are being therapeutically anticoagulated with an agent such as Coumadin (warfarin sodium) or subcutaneous heparin may be included provided there is no prior evidence of underlying abnormality in coagulation parameters, screening test results are in appropriate therapeutic range, and anticoagulation regimen is stable and closely monitored.
6. An expected survival of at least 6 months.
7. Male and female subjects must agree to use a highly reliable method of birth control (expected failure rate less than 5% per year) from the screening visit through 28 days after the last dose of study drug.

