12.0 Safety Endpoints

Safety will be assessed from records of AEs, laboratory values (clinical chemistry, hematology and urinalysis), vital signs, 12-Lead electrocardiogram (ECG) and results of physical examination. Severity of adverse events as determined by NCI Common Terminology Criteria for Adverse Events (CTCAE) v4.03.

All safety analyses will be conducted on the SAF population.

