15.1 List of Tables

| Table Number | Table Title | Population |
|----------------|--|-------------------------------|
| Table 14.1.1 | Patient Disposition | Safety Population |
| Table 14.1.2 | Protocol Deviations | Safety Population |
| Table 14.1.3 | Demography | Safety Population |
| Table 14.1.4 | Medical History | Safety Population |
| Table 14.1.5 | Oncology History | Safety Population |
| Table 14.1.6 | Oncology History – Time Since Diagnosis, Disease Status and Staging | Safety Population |
| Table 14.1.7 | Previous Medications | Safety Population |
| Table 14.1.8 | Concomitant Medications | Safety Population |
| Table 14.1.9 | Prior Cancer Treatment | Safety Population |
| Table 14.2.1 | Best Overall Response | Activity Evaluable Population |
| Table 14.2.2 | Progression-free Survival (Kaplan-Meier Analysis) | Activity Evaluable Population |
| Table 14.3.1 | Exposure | Safety Population |
| Table 14.3.2.1 | Overall Adverse Event Summary | Safety Population |
| Table 14.3.2.2 | Adverse Events by System Organ Class and Preferred Term | Safety Population |
| Table 14.3.2.3 | Treatment Emergent Adverse Events by System Organ Class and Preferred Term | Safety Population |

| Table Number | Table Title | Population |
|-----------------|---|-------------------|
| Table 14.3.2.4 | Drug-Related Treatment Emergent Adverse Events by System Organ Class and Preferred Term | Safety Population |
| Table 14.3.2.5 | Serious Adverse Events by System Organ Class and Preferred Term | Safety Population |
| Table 14.3.2.6 | Drug-Related Serious Adverse Events by System Organ Class, Preferred Term | Safety Population |
| Table 14.3.2.7 | CTC Grade 3 or greater Adverse Events by System Organ Class, Preferred Term | Safety Population |
| Table 14.3.2.8 | Drug-Related CTC Grade 3 or Greater Adverse Events by System Organ Class and Preferred Term | Safety Population |
| Table 14.3.2.9 | Adverse Events Leading to Discontinuation by System Organ Class and Preferred Term | Safety Population |
| Table 14.3.2.10 | Summary of Injection Site Reactions | Safety Population |
| Table 14.3.2.11 | Summary of Injection Site Reactions by Type and Severity | Safety Population |
| Table 14.3.2.12 | Summary of Injection Site Reactions by Type and Relationship | Safety Population |
| Table 14.3.3.1 | Shift from Baseline to Worst Post-Baseline Value (Low/High) for Clinical Chemistry Parameters | Safety Population |

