| Table 14.3.3.2 | Shift from Baseline to Worst Post-Baseline Value (Low/High) for Hematology Parameters | Safety Population |
| Table 14.3.3.3 | Summary of Absolute and Change from Baseline Value for Urinalysis Results | Safety Population |
| Table 14.3.4 | Summary of Absolute and Change from Baseline Value for Vital Sign Parameters | Safety Population |
| Table 14.3.5.1 | Summary of Absolute and Change from Baseline Value for ECG Parameters | Safety Population |
| Table 14.3.5.2 | Summary of ECG Findings | Safety Population |

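### Chemistry and hematology values are summarised only as (Low/High) shifts, although the entry criteria admit values already above ULN, so the summary tables can mask laboratory worsening

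*SAP*

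**What the plan says.** SAP 12.3 summarises blood chemistry and hematology in one way: "Shift tables will be constructed for the clinical chemistry and hematology data showing the shift from the baseline value to the worst" value after baseline, where worst means the minimum or maximum. The categories appear only in the table titles in SAP 15.1:

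- Table 14.3.3.1: "Shift from Baseline to Worst Post-Baseline Value (Low/High) for Clinical Chemistry Parameters"
- Table 14.3.3.2: "Shift from Baseline to Worst Post-Baseline Value (Low/High) for Hematology Parameters"

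For urinalysis the plan goes further: "The absolute value and the change from baseline will be tabulated for each scheduled time-point during the study for all continuous urinalysis parameters". SAP 12.4 and 12.5 also give absolute and change-from-baseline summaries for vital signs and ECG. Nothing similar is planned for blood tests, and no laboratory table uses CTCAE grades. The SAP mentions that scale for adverse events: "Severity of adverse events as determined by NCI Common Terminology Criteria for Adverse Events (CTCAE) v4.03" (SAP 12.0).

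Inclusion criterion 5 (Protocol 7.1) sets several limits as multiples of ULN. AST and ALT may be up to 2.5 x ULN. The criterion continues "For subjects with documented liver metastases, ALT and AST" may be up to 5 x ULN. Creatinine may be up to 1.5 x ULN. Total bilirubin must be below 1.5 x ULN, as must INR and PTT in patients not on therapeutic anticoagulation. Lymphocytes must exceed 700/mm³.

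**The concern.** A shift table against the reference range shows whether a value crossed a limit. It does not show how far past the limit the value went. That is a poor match for a population that may enter already past it. A patient who starts High can only be High to High on further worsening, which a reader takes as no shift.

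Safety and tolerability is the primary objective. Elsewhere the protocol works with degrees of abnormality: the retreatment criteria in 8.2.6 use multiples of ULN, and the DLT definition in 6.2.4 uses Grade 3 or greater. Liver and blood-count effects are also foreseen. Protocol 5.3.1 cites an intravenous IL-12 trial in which 65% of subjects had leukopenia and 47% had hyperbilirubinemia and elevated AST. What is at stake is whether the laboratory summary tables can show the size of such changes.

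**Working it through.** The plan states no figure on this point, so there is none to reproduce. The check classifies baseline and worst values against the reference range, starting from the entry limits.

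**Rule (assumed from the titles).** Low if below the lower limit, High if above ULN, otherwise Normal.

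**Inputs.** Baselines at or within the limits in Protocol 7.1; worst values are illustrative. The entry limits apply at screening. A value above ULN can be the baseline whether that means the screening value or the last value before first dose.

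| Test | Baseline (x ULN) | Worst (x ULN) | Fold rise | Cell |
|---|---|---|---|---|
| AST/ALT, no liver metastases | 2.5 | 2.5 | 1 | High to High |
| AST/ALT, no liver metastases | 2.5 | 25 | 25/2.5 = 10 | High to High |
| AST/ALT, liver metastases | 4 | 20 | 20/4 = 5 | High to High |
| Creatinine | 1.5 | 6.0 | 6.0/1.5 = 4 | High to High |
| Bilirubin | 1.49 | 5.96 | 5.96/1.49 = 4 | High to High |
| ALT, normal at baseline | 0.8 | 1.6 | 1.6/0.8 = 2 | Normal to High |
| ALT, normal at baseline | 0.8 | 8.0 | 8.0/0.8 = 10 | Normal to High |

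The first five rows share one cell, although the rises range from none to ten-fold. The last two also share one cell. So the table hides worsening when the baseline is raised, and hides severity when the baseline is normal. INR and PTT follow the same logic.

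**Hematology.** The entry floors are absolute values, and the documents give no lower limits of normal. The result therefore depends on an assumption. Take a lymphocyte count of 701/mm³ at entry:

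- Lower limit assumed anywhere from 800 to 1,500/mm³: the baseline is Low, and falls to 500, 200 or 100 all read Low to Low.
- Lower limit assumed at 600/mm³: the baseline is Normal and a shift shows, but the three falls still share one cell.

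**Cohort size.** SAP 1.0 reports cohorts of 3, 3, 3 and 4 patients in Phase I and 4, 4, 3 and 2 in Phase II, so 13 + 13 = 26 treated. One masked patient would be 1/4 = 25% to 1/2 = 50% of a cohort of four or two. This indicates scale only. The documents do not say how many patients had a raised baseline.

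**The hematology list.** SAP 12.3 names 14 hematology tests, including basophils, eosinophils and neutrophils. Lymphocytes are not among them, but the cell between basophils and eosinophils is blank in the text as read.

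**The case against.** Four arguments on the other side have weight.

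1. *The categories are inferred.* The sentence in SAP 12.3 names none, and (Low/High) in the titles could mean the direction of the worst value, matching minimum or maximum. That reading is possible. Low/Normal/High is the more natural one, and the H and L flags planned for the listings point the same way. If direction is what is meant, the categories are simply unspecified and still need stating.

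2. *Severe changes have a graded route.* Protocol 9.1 counts significant changes from baseline in laboratory results as adverse events, without requiring a limit to be crossed. These are graded by CTCAE v4.03. Grade 3 or greater events are tabulated (Tables 14.3.2.7 and 14.3.2.8), and DLTs appear in the overall summary. This stands as real mitigation. It depends on the investigator reporting the change as an event, and Protocol 10.3.2 speaks more narrowly of clinical manifestations of abnormal values. A graded laboratory table would be an independent check.

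3. *Every value is listed* with reference ranges, flags and clinical significance, and only 26 patients were treated. A careful reader could recover the severity. That stands too, and limits the loss to the summary tables.

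4. *The largest examples need liver metastases.* Baselines above 2.5 x ULN are admitted only with them. Correct, but the masking already applies at any baseline above ULN.

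A reader might infer that the comparison between doses is biased. The documents do not support that. SAP 9.0 plans no inferential statistics, and SAP 1.0 and 4.4 attribute the Phase II dose reductions to DLTs, not to these tables.

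A reader might also infer that lymphocytes were left out of the plan. That cannot be concluded either: the blank cell may be text lost in reading the PDF, and the shift-table sentence covers the hematology data without expressly restricting it to the list.

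**Conclusion.** The point holds for the summary tables. The only planned summaries of chemistry and hematology values are shifts labelled (Low/High). On the natural reading these show no shift when a patient admitted above ULN worsens, and do not separate mild from severe rises in patients who start normal.

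That patients may enter above ULN is certain from the documents for AST/ALT, creatinine, bilirubin and INR/PTT. For hematology it depends on site reference limits that the documents do not give. The conclusion assumes Low/Normal/High categories. How many patients are affected is unknown.

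This is a weakness in how laboratory safety is summarised, partly offset by the listings and the adverse event tables. It is not evidence that toxicity goes unrecorded or that any dose decision was wrong. Lymphocytes are a matter for confirmation. They deserve it because they are an entry and retreatment criterion, the protocol collects the differential count, and it reports of intratumoral adenoviral IL-12 vectors that "AEs were transient, with fever, malaise, sweating, and lymphopenia being the most common AEs observed".

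**What to change.** In SAP 12.3, define Tables 14.3.3.1 and 14.3.3.2 as shifts from baseline CTCAE v4.03 grade to worst post-baseline grade for every gradable test, with low and high directions shown separately. Keep Low/Normal/High for tests without a grade, and state those categories in the text as well as in the titles.

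Separately, check the hematology list against the source file and confirm that absolute lymphocytes are in it and in Table 14.3.3.2. Add them if they are not.

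No new data are needed: values and site reference ranges are already held, and CTCAE v4.03 is already the trial's severity scale. The cost is some reprogramming and wider tables. Worsening within a single grade would still not show, so the listings remain necessary.
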